1.2 Purpose

The purpose of this extension study (up to 104 weeks of treatment and up to 52 weeks of post-treatment follow-up) is to establish efficacy and safety of ligelizumab (QGE031) 120 mg s.c. q4w. This will be assessed in adult and adolescent CSU patients who have completed one of the studies CQGE031C2302, CQGE031C2303, CQGE031C2202 or CQGE031C1301 (the "preceding studies") and who have relapsed, following treatment in these preceding studies, despite standard of care treatment with H1-antihistamines (H1-AH) (at local label approved doses), in the following scenarios:

- re-treatment with ligelizumab 72 or 120 mg s.c. q4w following treatment in the preceding studies;
- self-administration of ligelizumab 120 mg s.c. q4w outside of the clinic setting;

- ligelizumab 120 mg s.c. q4w used as monotherapy, i.e. when background H1-AH medication is discontinued

[figure not shown]
[figure not shown]
In addition, this study will evaluate whether ongoing long-term treatment drives drug-mediated remission of disease. This study will also fulfill the Novartis commitment to provide post-trial access to patients who have completed studies CQGE031C2302, CQGE031C2303, CQGE031C2202 or CQGE031C1301.

[figure not shown]
[figure not shown]
2 Objectives and endpoints

Table 2-1 Objectives and related endpoints

Objective(s)	Endpoint(s)
Primary objective(s)	Endpoint(s) for primary objective(s)

 • To evaluate the efficacy of retreatment with ligelizumab 72 mg or 120 mg q4w in subjects previously treated in the core studies (CQGE031C2302/CQGE031C2303) 
 • To evaluate the efficacy of retreatment with ligelizumab in the subgroup of these subjects who achieved a weekly urticaria activity score (UAS7) ≤ 6 after 12 weeks of treatment in these core studies 	
 • The proportion of subjects with well-controlled disease (UAS7 ≤ 6) at Week 12
Secondary objective(s)	Endpoint(s) for secondary objective(s)
For retreatment efficacy evaluation:	

 • To describe the efficacy of ligelizumab 72 mg or 120 mg q4w in achieving complete control of chronic spontaneous urticaria (CSU) at Week 12 when used as retreatment for subjects previously treated in the core studies (CQGE031C2302/CQGE031C2303) • To describe the efficacy of ligelizumab with respect to a reduction from extension study baseline in the UAS7 and its components (weekly itch severity score (ISS7) and weekly hives severity score (HSS7) at Week 12 in all subjects receiving the same dose regimen as in the core studies, i.e. 72 mg or 120 mg q4w • To describe the efficacy of ligelizumab in achieving an angioedema-free period at Week 12 in all subjects receiving the same dose regimen as in the core studies, i.e. 72 mg or 120 mg q4w • To describe the efficacy of ligelizumab in achieving Dermatology Life Quality Index 	
 • The proportion of subjects with completely controlled disease (UAS7 = 0) at Week 12 • Absolute change from extension study baseline in the UAS7 and its components (ISS7 and HSS7) at Week 12 • Cumulative number of weeks that subjects achieve weekly angioedema activity score (AAS7) = 0 between extension study baseline and Week 12 • Percentage of subjects achieving DLQI = 0-1 at Week 12

Objective(s)	Endpoint(s)
(DLQI) = 0-1 at Week 12 when used as re-treatment for all subjects receiving the same dose regimen as in the core studies, i.e. 72 mg or 120 mg q4w	
For self-administration efficacy evaluation:	

To describe the efficacy of ligelizumab in the treatment of CSU, 12 weeks after starting self-administration	
The proportion of subjects with well-controlled disease ($UAS7 \leq 6$), 12 weeks after starting self-administration
For safety & tolerability evaluation:	

To assess the safety and tolerability of ligelizumab in all subjects	
In each dose group, and for each duration of treatment:
 
Occurrence of treatment emergent adverse events during the studyOccurrence of treatment emergent serious adverse events during the studyVital signsLab assessments

To assess the safety and tolerability of ligelizumab 120 mg q4w 1mL pre-filled syringe (PFS)	
For the duration of treatment:
 
Occurrence of treatment emergent serious adverse events during study Week 12 onwardsVital signs Week 12 onwardsLab assessments Week 12 onwards

To assess the safety and tolerability of ligelizumab 120 mg q4w in all subjects who self-administer	
Occurrence of treatment emergent adverse eventsOccurrence of treatment emergent serious adverse eventsVital signsLab assessments

3 Study design

This is a Phase IIIb multi-center, double-blinded and open-label, extension study to evaluate efficacy and safety of ligelizumab 72 mg and 120 mg s.c. q4w as add-on therapy to H1-AHs with an option for monotherapy i.e. with discontinuation of background H1-AH in adult and adolescent CSU subjects who have completed one of the CQGE031C2302, CQGE031C2303, CQGE031C2202 or CQGE031C1301 studies (“preceding studies”), in the setting of retreatment and self-administration.

As per [Table 1-1](#), the definition of the disease states for CSU, for purposes of this study protocol and used for decisions described in this section is:

- Urticaria-free (Completely controlled disease): $UAS7 = 0$;
- Well controlled disease: $UAS7 \leq 6$;
- Mild Disease: $UAS7 > 6$ and < 16 and
- Moderate to severe disease: $UAS7 \geq 16$.

As depicted in [Figure 3-1](#), the study consists of 5 distinct periods

- Screening period (Day -28 to Day -7), duration 1 to 4 weeks;
- First observation period, duration up to 36 weeks;
- Treatment period, duration of 2 years (104 weeks);
- Second observation period, duration up to 52 weeks;
- Post-treatment follow-up period, duration of 12 weeks or 52 weeks.

The minimum duration of a subject’s stay in the study without early discontinuation is approximately 37 weeks: 1 week screening plus 36 weeks in first observation period until the subject exists the study without a relapse.

The maximum duration of a subject’s stay in the study without early discontinuation is approximately 208 weeks: 4 weeks screening, 36 weeks in first observation period, 52 weeks in first half of the treatment period, 52 weeks in the second half of the observation period, 52

weeks in second half of the treatment period and 12 weeks in the follow-up period until the subject exits the study.

If the study site is ready to enroll subjects in the extension study, and the subject completed the preceding study's End of Study Visit (EOS, Visit 1999), the subject can "roll-over" into this extension study. When the site is ready to enroll subjects, the subject should be enrolled into the extension study in as short time-frame as possible. Subsequently, all subjects who refuse participation in the extension study at the time of V1999 will not be allowed to enter at a later time unless there are circumstances beyond their control. All assessments done as a part of Visit 1999 for preceding studies will be considered for screening for the extension study. These subjects will have their Screening Visit 1 for the extension study on the same day as Visit 1999 of the preceding study.

Subjects who complete Visit 1999 of the preceding studies prior to the study site being ready to enroll subjects in the extension study, will have a gap between their Visit 1999 and Screening Visit 1 i.e. Visit 1999 and screening Visit 1 will not occur on the same day. Informed consent for the extension study will be signed off prior to or at Screening Visit 1. If this gap between the two visits is less than or equal to 30 days, all Visit 1999 assessments can still be used to determine eligibility into the extension study. If this gap between the two visits exceeds 30 days, subjects will be re-assessed for eligibility into the trial at Screening Visit 1. During this gap between completion of preceding studies and enrolment into extension study:

- Subjects can use second generation H1-AH as per CSU treatment guidelines.
- Subjects can use omalizumab, if needed, provided there is at least 16 weeks between last dose of omalizumab and Visit 101 or V201.
- Subjects can use oral corticosteroids, if needed, provided there is at least 30 days between last dose of oral corticosteroid and Screening Visit 1 of this study.

[figure not shown]
[figure not shown]

Figure 3-1 Study design

¹ After screening, UAS7 score will be assessed via eDiary

² Subjects from C2302/2303 72 mg dose arm will receive the 72 mg; all other subjects will receive ligelizumab 120 mg

³ Blinded to core study treatment group but unblinded to observation period

⁴ Subjects completing 104 continuous weeks of treatment enter 52-week follow up; All other subjects enter 12-week follow up

EP = Endpoint; SCR = screening; LIVI = liquid in vial; PFS = prefilled syringe

---> Treatment continuation decision: PI reassessment in discussion with subject

★ Week 12 Self-admin: Qualifying subjects starts self-admin in clinic at Wk 12 and transitions at Wk 24 to out of the clinic setting

‡ Week 64 Repeat & new self-admin: Subjects re-starting self-admin at Week 64 and subjects who newly qualify, will start self-admin in clinic at Week 64 and transition at Week 76 to out of the clinic setting

◼ Ligelizumab monotherapy: Subjects with UAS7 ≤ 6 at Week 52, who re-enter 2nd half of treatment period from the 2nd observation period, will have a possibility to discontinue H1-AH background medication at Week 64, per investigator's discretion taking into account if CSU symptoms are well controlled

3.1 Screening period

For all study participants, the first visit of the extension phase at Visit 1 should occur on the same day as the preceding studies' EOS visit (Visit 1999), or in as short time-frame as possible after the Visit 1999 of the preceding studies, as described below.

- At or prior to Visit 1, (Visit 1999 of the preceding studies, if the subject is transitioning immediately), eligible subjects will sign an informed consent form (ICF).
- All lab assessments performed at Visit 1999 (if not more than 30 days prior to the extension screening Visit 1) and all other required assessments as per extension study protocol will be used to determine eligibility to enroll into this extension study. If the gap between the Visit 1999 of preceding studies and extension screening Visit 1 is greater than 30 days, then all lab and other required assessments will need to be re-done at extension screening Visit 1.
- Subjects must remain on the same H1-AH background medication they were taking in the preceding studies.
- Subjects should use the same H1-AH rescue medication that was agreed with the investigator at Visit 1 of this study.
- Use of oral corticosteroid rescue medication is not permitted during the screening period.
- Subjects' relevant medical conditions and concomitant medications will be reviewed at Visit 1 (Visit 1999 of the preceding studies, if the subject is transitioning immediately to the extension study).
- The subjects will continue to complete all eDiary assessments, including assessment of UAS. The 7 days prior to Week 0 will be used to calculate the UAS7 score:
 - If the subject has moderate to severe disease, defined as $UAS7 \geq 16$, the subject will enter the treatment period immediately at Visit 201 (Week 0) to start treatment, as described in [Section 3.3](#).
 - If the subject has a UAS7 of < 16 , the subject will transition to the first observation period at Visit 101 (Week 0), as described in [Section 3.2](#).

Rescreening may be allowed for subjects who fail initial screening (see [Section 5.1](#) and [Section 5.2](#) on when rescreening is allowed). Only one rescreening will be allowed. If a subject is rescreened for the study, the subject must sign a new informed consent and will be issued a new subject number. Informed consent for a rescreened subject must be obtained prior to performing any study-related assessments or collecting any data for the Screening Visit.

3.2 First observation period

- Visit 101 (Week 0) to 199 (Week 36 also referred to as End of Observation Period 1/EOOBS1).
- If the subject's UAS7 is < 16 at Week 0, the subject will enter the first (investigational treatment-free) observation period, performing assessments for Visit 101 after which they will be assessed remotely (i.e. outside the clinic) by a safety phone call from the site every 4 weeks, unless there is an in-clinic visit scheduled.
- Subjects will have in-clinic safety and efficacy assessments done at 12-week intervals.

- Subjects must remain on the same H1-AH background medication they were taking in the preceding studies.
- Subjects should use the same H1-AH rescue medication that was agreed with the investigator at Visit 1 of this study.
- Use of oral corticosteroid rescue medication is **not permitted** during this first observation period.
- Subjects will continue to complete the eDiary twice daily as per protocol, in order to monitor the activity of their disease.
- Subjects who present with moderate to severe active disease ($UAS7 \geq 16$; having at least 12 out of 14 records for HSS and ISS respectively completed in one assessment week during observation) will be brought back to clinic as soon as possible:
 - a. Subjects will perform the Visit 201 if they had Visit 1 in the last 30 days.
 - b. Subjects for whom Visit 1 occurred more than 30 days ago will perform assessments from screening Visit 2. Assessments from Visit 2 will be used to determine eligibility as applicable (see [Section 5.2](#)).
- Subjects with $UAS7 < 16$ by the end of this first observation period will perform Visit 199 (EOOBS1) of this extension study to exit the study.
- Subjects who wish to discontinue from the first observation period and study, will be expected to complete Visit 199 (EOOBS1).

3.3 First half of the treatment period

- Week 0 (Visit 201) to Week 52
- Subjects receive their first dose of ligelizumab at Visit 201 (Week 0) and last dose of ligelizumab of this first half of the treatment period at Visit 213 (Week 48).
- Subjects must remain on the same H1-AH background medication they were taking in the preceding studies.
- Subjects should use the same H1-AH rescue medication that was agreed with the investigator at Visit 1 of this study.
- Oral corticosteroid rescue medication is permitted only at and after Visit 204 (Week 12) (after all assessments are completed), with the limitations as per protocol (see [Section 6.2.3](#)).
- Subjects entering the first half of the treatment period from the preceding studies will be assigned to treatment as follows:
 - Core studies CQGE031C2302 and CQGE031C2303:
 - For the first 12 weeks, the blinded treatment assignment will be determined according to the treatment group assignment during the core studies following these rules:
 - Subjects treated with ligelizumab 72 mg liquid in vial s.c. q4w in the core studies will be treated with ligelizumab 72 mg liquid in vial s.c. q4w in a double-blind manner such that their prior treatment regimen will not be unblinded.
 - All other subjects from the core studies will be treated with ligelizumab 120 mg liquid in vial s.c. q4w in a double-blind manner such that their prior treatment regimen will not be unblinded.

- Studies CQGE031C1301 and CQGE031C2202:
 - All subjects from these studies will be treated with ligelizumab 120 mg liquid in vial s.c. q4w in an open-label manner for the first 12 weeks.
- If the subject in the screening period or first observation period presents with moderate to severe disease, defined as $UAS7 \geq 16$, the subject will enter the treatment period at Visit 201 (Week 0), and start the treatment assigned as above.
- At Visit 204 (Week 12), all subjects will be switched to ligelizumab 120 mg s.c. pre-filled syringe (PFS) q4w in an open-label manner.
- At Visit 204 (Week 12) subjects will be offered an opportunity to administer ligelizumab outside the clinic. For details regarding self-administration outside of the clinic and monitoring post ligelizumab administration, see [Section 6.7.2](#).
- All subjects, whether in the clinic-administered or outside the clinic self-administered group will continue to complete the eDiary twice daily as per protocol.
- All subjects should complete their eDiary for the 7 days prior to Visit 214 (Week 52) to ensure the UAS7 thresholds are available for evaluation at Visit 214 (Week 52).
- At Week 52 UAS7 needs to be assessed:
 - Subjects who have achieved a $UAS7 \leq 6$ will transition to the second observation period Visit 301 (see [Section 3.4](#)).
 - Subjects who have achieved a $UAS7 > 6$ and < 16 will continue treatment without interruption into the second half of the treatment period (Visit 214), unless a decision to stop treatment is made based on a risk-benefit discussion between the investigator and subject, in which case the subject would move to the second observation period Visit 301).
 - For subjects with a $UAS7 \geq 16$, the investigator must reassess the risk-benefit with the subject and decide whether the subject will continue with the investigational treatment (Visit 214) or move to the follow-up period and perform Visit 9998 (see [Section 4.2](#) – Rationale for duration of treatment).

3.4 Second observation period

- Visit 301 (Week 0) to 399 (Week 52 also referred to as End of Observation Period 2, EOBS2).
- If the subject's UAS7 is ≤ 6 at Week 52, the subject will enter the second (investigational treatment-free) observation period Visit 301 (Week 0) and will be assessed remotely (i.e. outside the clinic) by a safety phone call from the site every 4 weeks, unless there is an in-clinic visit scheduled.
- Subjects will have in-clinic safety and efficacy assessments done at 12 or 16 week intervals.
- Subjects must remain on the same H1-AH background medication they were taking in the preceding studies.
- Subjects should use the same H1-AH rescue medication that was agreed with the investigator at Visit 1 of this study.
- Use of oral corticosteroid rescue medication is **not permitted** during this second observation period.

- Subjects will continue to complete the eDiary twice daily as per protocol, in order to monitor the activity of their disease. All subjects should complete their eDiary for the 7 days prior to Visit 214 (i.e. one assessment-week) to ensure the UAS7 thresholds are available.
- Subjects who present with moderate to severe active disease ($UAS7 \geq 16$) will be brought back to clinic to be treated as soon as possible to perform Visit 214 (Week 52) in the second half of the treatment period) and restart treatment with ligelizumab 120 mg PFS q4w.
- Subjects with a $UAS7 < 16$ by the end of this second observation period will perform Visit 399 (EOOBS2) of this extension study to exit the study.
- Subjects who wish to discontinue from this observation period will be expected to complete at least Visits 301, 302 and 303 (Week 0, 4 and 8), and perform Visit 399 (Week 52/EOOBS2) and exit the study.

3.5 Second half of treatment period

- Visit 214 to 9998 (Week 52 to Week 104)
- At Week 52:

Subjects who have achieved **UAS7 of > 6 and < 16** will be assessed based on a risk-benefit discussion between the subject and the investigator on whether to continue treatment without interruption into the second half of the treatment period, or, move to the second observation period.

- These subjects, with an uninterrupted treatment period of 104 weeks will complete the second half of the treatment period at Visit 9998 (Week 104/EOT (End of Treatment)), and transition to the 52-week follow-up period Visit 501 (Week 116).
- These subjects will not be allowed to discontinue H1-AH background medication.

For subjects who have achieved a **UAS7 ≥ 16** , the investigator must reassess the risk-benefit with the subject. This discussion with the individual subject will include whether or not the subject has had enough improvement from their initial disease state at the start of the treatment period, even though they still have moderate to severe disease, to justify continuing in the treatment period.

Based on this benefit risk assessment and discussion with the subject, the subject and investigator will decide whether to

- continue with the investigational treatment (ligelizumab 120 mg s.c. q4w PFS) in the second half of the treatment period **or**
- discontinue the treatment, and complete Visit 9998 (Week 104/EOT) and transition to the 12-week follow-up period Visit 9999 (Week 156/EOS).
- These subjects will not be allowed to discontinue H1-AH background medication.

For the sub-group of subjects who achieved a **UAS7 ≤ 6** at Week 52, and re-entering treatment (second half of the treatment period) from the second observation period due to a relapse ($UAS7 \geq 16$):

- These subjects must enter the second half of the treatment period at Visit 214 (Week 52).
- At Visit 403 (Week 64), only this sub-group of subjects will be offered the opportunity, after discussion with the investigator, to discontinue their H1-AH background medication (i.e. ligelizumab 120 mg s.c. q4w PFS monotherapy).

- To support the investigator in making the decision for monotherapy, subjects should complete their eDiary for the 7 days prior to Visit 403 (i.e. one assessment-week) to ensure the UAS7 thresholds are available.
- The investigator will decide whether monotherapy is appropriate considering the UAS7 score. It is recommended that only subjects with $UAS7 \leq 6$ at Visit 403 (Week 64) discontinue H1-AH.
- These subjects must be advised that, if needed to use their H1-AH background medication, they must then remain on their H1-AH background medication for the rest of the study. Any worsening of CSU symptoms can be managed with the use of H1-AH rescue medication without the need to resume H1-AH background medication.
- All subjects completing the second half of the treatment period will complete the Visit 9998 (Week 104/EOT), and transition to the 12-week follow-up period Visit 9999 (Week 156/EOS).
- All subjects, whether in the clinic-administered or outside the clinic self-administered group will continue to complete the eDiary twice daily as per protocol.
- Subjects should use the same H1-AH rescue medication that was agreed with the investigator at Visit 1 of this study.
- Use of oral corticosteroid rescue medication is permitted during the second half of the treatment period, with the limitations as per [Section 6.2.3](#).
- For details regarding monitoring post ligelizumab administration and self-administration outside of the clinic, see [Section 6.7.2](#).

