3.6 Follow-up period

- Visit 501 to 9999 (Week 116 to Week 156)
- Subjects who do not complete a continuous 104-week treatment will enter the follow-up period for 12 weeks duration and will only perform Visit 9999 (Week 156).
- Subjects who have completed the full 104-week treatment period without interruption will enter the follow-up period of 52 weeks duration and will perform Visit 501 to Visit 9999 (Week 116 to Week 156).
- After completion of the follow-up period, subjects will perform the EOS visit (Visit 9999) and exit the study.
- Subjects will continue to complete the eDiary twice daily as per protocol (see [Table 8-1](#)), in order to monitor the activity of their disease.
- Subjects who decided to remain on H1-AH background medication will continue to use H1-AH background medication. Subjects who decided to go off H1-AH background medication should continue to remain off.
- Subjects should use the same H1-AH rescue medication that was agreed with the investigator at Visit 1 of this study.
- Use of oral corticosteroid rescue medication is permitted during the follow-up period, with the limitations as per protocol (see [Section 6.2.3](#)).

4 Rationale

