Adolescents will be included in this study, as they make up all, or part of the, study population in the CQGE031C2202 and CQGE031C2302 / CQGE031C2303 studies, respectively, and as CSU appears to be the same condition with the same unmet medical need in both adult and pediatric populations. The symptoms and natural course of CSU are very similar in both age groups (Church et al 2011), (Caffarelli et al 2013). This Phase 3 extension study will provide further support for long-term efficacy and safety in the adolescent population.

The timepoint for the primary endpoint analysis (Week 12, Visit 204) in this study is chosen to align with that in the Phase 3 core studies, allowing the comparison of retreatment efficacy following 72 mg and 120 mg s.c. q4w.

[REDACTED]

The 52-week post-treatment follow-up period (12-weeks for subjects completing less than 104 weeks of continuous treatment) will assess safety following treatment discontinuation, as well as evaluate long-term treatment outcome including sustained remission.

To allow an adequate follow-up of approximately 5 half-lives following the last dose administration, a 12-week follow-up period is expected for:

- Subjects discontinuing in the treatment periods
- Subjects discontinuing in the second observation period

This Phase 3 double-blind and open-label extension study will evaluate the efficacy of ligelizumab in the management of CSU from three aspects:

- First, in order to evaluate the retreatment, long-term efficacy and safety with ligelizumab, subjects with moderate to severe disease (defined as $UAS7 \geq 16$) will be enrolled directly after the screening period as described in Section 3.3. If subjects do not have moderate to severe disease at the time of screening, they will move to the first observation period (see Section 3.2). During this period, they will be monitored for disease activity and safety assessments through a combination of safety phone calls from the sites and in-clinic visits, as per the assessment / visit schedule (Table 8-2). Once they reach the threshold of $UAS7 \geq 16$, they will return to the site as soon as possible to be enrolled to treatment as described in Section 3.3. In this way, all subjects eligible to transition from the preceding studies will be assessed in the screening period and start treatment within as short a time as possible once they present with moderate to severe disease, or they will be closely followed until they qualify for treatment.

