¹⁵ Detailed arrangements for safety phone calls on a regular basis per protocol must be planned at Visit 207 (Week 24) for all subjects self-administering investigational drug and safety phone call will replace visits at site for these subjects.

¹⁶ IRT to dispense kits to take with them for subjects who do self-administration.

¹⁷ (a) Continuation of treatment and (b) Restarting of treatment for subjects relapsing in the second observation period

¹⁸ Transcribe results from Visit 1999 of the preceding studies to screening eCRF if Visit 1999 date and Screening Visit 1 date are less than or equal to 30 days apart. If Visit 1999 date and Screening Visit 1 date are more than 30 days apart assessment has to be repeated.

¹⁹ In the event that the 3 stool samples from Visit 1999 of the preceding studies were not collected, or the results from these are not available, or Visit 1999 date and Screening Visit 1 date are more than 30 days apart, subjects must be assessed at Visit 1 (see [Section 8.4.4](#)).

²⁰ Hematology and chemistry results will be transcribed automatically by central lab from Visit 1999 to Visit 1. Urine dipstick results need to be transcribed to the respective eCRF.

²¹ INR (International Normalized Ratio) at Visit 201 and unscheduled Visit only

²² hCG for all female subjects of child-bearing potential at Visit 1 only

²⁴ Urine pregnancy tests will be provided to all self-administration subjects who are women of child-bearing age, for home use. In the event that the home test is positive, the subject must call site and arrange for an immediate visit to perform a serum pregnancy test.

²⁵ Transcribe weight for adults and adolescents from Visit 1999 of the preceding studies to screening eCRF; If Visit 1999 date and Screening Visit 1 date are more than 30 days apart assessment has to be repeated. Transcribe height for adolescents from Visit 1999 of the core phase 3 studies and CQGE031C2202 to screening eCRF; If Visit 1999 date and Screening Visit 1 date are more than 30 days apart assessment has to be repeated. Measure height for adult subjects and record on screening eCRF.

²⁶ (a) Subjects who complete all visits on investigational drug during the 104 weeks treatment period without interruption will complete a 52 weeks post-treatment follow-up period. (b) all other subjects will complete a 12 week post-treatment follow-up period. For all subjects last visit is EOS/9999.

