8.3.3 Appropriateness of efficacy assessments

At the time the omalizumab studies were carried out, the treatment paradigm focused primarily on itch (ISS7) as a key symptom of CSU. Over the past several years the goal of therapy has evolved and the current target of therapy as described in the current CSU treatment guidelines (Zuberbier et al 2018) is to treat the disease until it is gone, i.e. complete control of the disease (UAS7 = 0). Given the current emphasis on UAS7 in the medical community and as reflected in the CSU treatment guidelines, data from the Phase 2 study CQGE031C2201 supported the change from baseline in UAS7 (which is a composite of ISS7 and HSS7) at Week 12 being assessed as the primary endpoint in the ongoing Phase 3 core studies. In this Phase 3 extension study, which is reflective of long-term real world management of CSU, the primary endpoint is well-controlled urticaria at Week 12 in the first half of the treatment period, assessed as percentage of subjects achieving $UAS7 \leq 6$. This is consistent with the longer-term realistic clinical goal of achieving well-controlled disease ($UAS7 \leq 6$), which also includes completely controlled disease ($UAS7 = 0$).

Disease recurrence after investigational drug is withdrawn will be measured during the post-treatment follow-up periods. Disease worsening, after well-controlled disease ($UAS7 \leq 6$) will be measured during the second observation period.

For all subjects, symptom scores will be measured during the observation, treatment and post-treatment follow-up periods.

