2.1.1.2 Study periods

The following study periods will be considered for analysis:

- Screening period (SCR): from the date of signing informed consent form (ICF) to, and not include the date of the first ligelizumab treatment (i.e. V201) in extension, or the first visit in the first observation period (i.e. V101), whichever comes first.
- First observation period (OBS1): from Visit 101 up to Visit 199. The duration of OBS1 period for each subject varies, as it depends on occurrence of relapse ($UAS7 \geq 16$). Maximum duration of OBS1 is 36 weeks.
- First 12 weeks of the first half of the treatment period (TRT1A): from Visit 201 to Visit 204.
- Week 12 to Week 52 of the first half of the treatment period (TRT1B): from Visit 204 to Visit 214 or 301, whichever comes first.
- Entire first half treatment period (TRT1): from Visit 201 to Visit 214 or 301, whichever comes first.
- Second observation period (OBS2): from Visit 301 up to Visit 399. The duration of OBS2 period for each subject varies, as it depends on occurrence of relapse ($UAS7 \geq 16$). Maximum duration of OBS2 is 52 weeks.
- Second half of the treatment period (TRT2): Visit 214 to Visit 9998 (excluding Visit 301 to Visit 399)
- Follow-up period:
 - Subjects who do not complete a continuous 104-week treatment will enter the follow-up period (FU12) for 12 weeks duration and will only perform Visit 9999.
 - Subjects who have completed the full 104-week treatment period without interruption will enter the follow-up period (FU52) of 52 weeks duration and will perform Visit 501 to Visit 9999 (Week 116 to Week 156).

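### A bullet in Protocol 3.5 sends every second-half completer to 12 weeks of follow-up, contradicting the 52-week rule for uninterrupted completers stated elsewhere in the protocol and SAP

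*Protocol*

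**What the plan says.** Near the end of Protocol 3.5, after the paragraphs on the three Week 52 groups, one bullet reads "All subjects completing the second half of the treatment period will complete the Visit 9998 (Week 104/EOT), and transition to the 12-week follow-up period". It has no qualifier.

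Earlier in the same section, subjects with UAS7 above 6 and below 16 at Week 52 who are treated for 104 weeks without interruption "will complete the second half of the treatment period at Visit 9998 (Week 104/EOT (End of Treatment)), and transition to the 52-week follow-up period".

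The general rule appears in several other places and depends only on continuity of treatment:

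- Protocol 3.6: "Subjects who have completed the full 104-week treatment period without interruption will enter the follow-up period of 52 weeks duration". The same section gives everyone else 12 weeks, with Visit 9999 only.
- Figure 3-1, footnote 4: "Subjects completing 104 continuous weeks of treatment enter 52-week follow up; All other subjects enter 12-week follow up".
- Protocol 4.1: "The 52-week post-treatment follow-up period (12-weeks for subjects completing less than 104 weeks of continuous treatment) will assess safety following treatment discontinuation".
- Table 8-1, footnote 26: "Subjects who complete all visits on investigational drug during the 104 weeks treatment period without interruption will complete a 52 weeks post-treatment follow-up period".
- SAP 2.1.1.2: "Subjects who have completed the full 104-week treatment period without interruption will enter the follow-up period (FU52) of 52 weeks duration". SAP 2.1.1.3.4 and footnote 4 to SAP Figure 1-1 agree.

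**The concern.** Read literally, the 3.5 bullet gives uninterrupted completers 12 weeks where the rest of the plan gives them 52. Subjects with UAS7 between 6 and 16 at Week 52 are protected by their own bullet in 3.5. Subjects with UAS7 of 16 or more are not. Section 3.5 lets them continue without a break after a risk-benefit discussion and states a 12-week follow-up for those who stop. For those who continue to Week 104, it gives no completion rule other than the unqualified bullet.

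At stake is off-treatment information. Protocol 4.1 gives the long follow-up the task of evaluating sustained remission, and Protocol 8.3.3 says "Disease recurrence after investigational drug is withdrawn will be measured during the post-treatment follow-up periods". A subject sent to the wrong period would have the end-of-study visit and stop the diary early. The corticosteroid rescue limit would also differ: 3 doses in the 12-week period against 9 in the 52-week period (Protocol 6.2.3). In addition, SAP 2.3.4 summarises the two follow-up periods separately, so the subject would not fit the SAP's period definitions.

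**Working it through.** **1. Related figure in the plan.** Protocol 3 gives a maximum stay of about 208 weeks. Adding its listed periods (screening, first observation, first treatment half, second observation, second treatment half, follow-up): 4 + 36 + 52 + 52 + 52 + 12 = 208. This reproduces. It is the interrupted path, for which 12 weeks is correct, so it does not support the bullet for uninterrupted subjects.

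**2. The rules side by side.**

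| Place | Uninterrupted 104 weeks | All others |
|---|---|---|
| 3.5, disputed bullet | 12 weeks | 12 weeks |
| 3.5, UAS7 > 6 and < 16 bullet | 52 weeks | not stated |
| 3.6 | 52 weeks | 12 weeks |
| Figure 3-1, footnote 4 | 52 weeks | 12 weeks |
| 4.1 | 52 weeks | 12 weeks |
| Table 8-1, footnote 26 | 52 weeks | 12 weeks |
| SAP 2.1.1.2 and 2.1.1.3.4 | 52 weeks | 12 weeks |

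Apart from the 3.5 bullet for the middle UAS7 group, none of the 52-week statements depends on the Week 52 score. The disputed bullet is the only outlier.

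**3. Visit timing.** From the scheduled days in Table 8-1, Visit 9998 to Visit 501 is (813 − 729)/7 = 12 weeks, and Visit 9998 to Visit 9999 is (1093 − 729)/7 = 52 weeks. In the 12-week period Visit 9999 keeps its nominal Week 156 label, but 12 weeks after Week 104 is Week 116 in elapsed time.

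**4. Last dose.** Protocol 6.6.1 gives 13 four-weekly injections in the second half: 52 + 12 × 4 = Week 100.

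**5. Loss per misrouted subject.**

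- End of the 12-week follow-up: 104 + 12 = Week 116, which is 116 − 100 = 16 weeks after the last dose.
- End of the 52-week follow-up: 104 + 52 = Week 156, which is 156 − 100 = 56 weeks after the last dose.
- Difference: 56 − 16 = 40 weeks, and 40/52 = 77% of the intended follow-up.
- Visits: 501, 502, 503 and 9999 (four) against 9999 alone (one), so three of four are lost.
- Twice-daily urticaria diary records: 40 × 7 × 2 = 560 at most.

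**6. What is not lost.** Protocol 12.5.2 counts adverse events as treatment-emergent up to 16 weeks after the last dose. A 12-week follow-up ends exactly 16 weeks after the last dose, so that window is covered under either rule.

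**7. After correction.** The 208-week maximum does not change. An uninterrupted subject with the longest screening and first observation periods stays 4 + 36 + 104 + 52 = 196 weeks, against 4 + 36 + 104 + 12 = 156 under the literal bullet.

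**The case against.** The best defence is that the bullet was meant only for subjects with UAS7 of 6 or less at Week 52 who relapse and re-enter treatment. It directly follows the monotherapy bullets for that group, 12 weeks is right for them, and they otherwise have no exit rule in 3.5. The extracted text has lost list indentation, so this reading cannot be excluded. The wording counts against it, however. The subgroup bullets refer back to their own subjects, while this one names all completers, and the bullet that follows it plainly applies to every subject. If the narrow reading is right, 3.5 still has no completion rule for uninterrupted subjects with UAS7 of 16 or more. The section needs an edit either way.

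The second defence is that Protocol 3.6 comes next, defines follow-up, and together with Table 8-1 covers those subjects. That is true. A careful site would probably follow 3.6 and Table 8-1, and the 40-week loss arises only if one did not. No document shows that it happened.

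Third, no primary or secondary efficacy endpoint listed in Protocol Table 2-1 uses the follow-up period. The study was terminated early, and SAP 2.14.1 drops the continuous long-term subpopulation from the final analysis. Subjects still at UAS7 of 16 or more after a year on drug are also unlikely to supply much of the remission data. These points limit the consequence but do not make the sentence correct.

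**Conclusion.** The concern holds as a minor inconsistency. As written, the bullet gives the wrong follow-up for anyone completing 104 weeks without interruption, and the other sections establish the intended rule beyond reasonable doubt. For each subject actually routed by it, 40 of 52 follow-up weeks would be lost. That size is conditional on a site applying the bullet over 3.6 and Table 8-1.

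The number of subjects affected cannot be derived and could be zero. The documents give neither the share with UAS7 of 16 or more at Week 52 nor the share of those who continue. Sample size, the primary analysis and the treatment-emergent adverse event window are unaffected.

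**What to change.** Restrict the bullet to subjects who did not receive 104 weeks of continuous treatment: Visit 9998, then the 12-week follow-up ending at Visit 9999. Add that every subject who completes 104 weeks without interruption, including those with UAS7 of 16 or more at Week 52, enters the 52-week follow-up (Visits 501 to 9999) under Protocol 3.6.

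The cost is one protocol sentence, with no change to the visit schedule, any analysis or the SAP. As the study has been terminated, a clarification or a note in the study report would do, together with a check on whether any uninterrupted completer was given only the 12-week follow-up.
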